9.5.3 Blood Sample Collection

Blood will be collected at the indicated time points to be processed and banked in the DF/HCC Clinical Trials Core laboratory for future research purposes. Blood samples are collected four ways:

- Streck Tubes
- Lavender Top Tubes
- PBMC/PAXgene Tubes
- Circulating Tumor Cells/CellSave tubes

These samples will be used to look at DNA, RNA and protein in future studies. Refer to the details below for scheduling, collection, processing, and shipping details.

Streck Tubes

One 10 mL Streck tube will be collected and processed at baseline and time of progression (all study Arms) for evaluation of cell free circulating DNA (cfDNA). Tubes are provided by the Sponsor as needed.

- If the baseline sample is missed for any reason, it should be drawn at a future appointment.
- **For Arm A patients:** The Cycle 2 Day 8 sample may be drawn +/- 3 days. Draw the Cycle 2 Day 9 research blood 18-48 hours after the Cycle 2 Day 8 research blood draw and on the same day as the cycle 2 research biopsy. If the Cycle 2 Day 9 biopsy is missed (i.e. due to scheduling problems, procedure cancellation, etc), then it should be performed instead on Cycle 2 Day 16 +/- 3 days, and the Cycle 2 research blood tests should be rescheduled to occur around the delayed biopsy (i.e. Cycle 2 Day 15 and Cycle 2 Day 16). If a patient on Arm A does not undergo the Cycle 2 biopsy, then the Cycle 2 Day 9 blood draw is not required. However, the patient is still required to undergo the Cycle 2 Day 8 research blood draw.
- **For Arm B patients:** Draw Cycle 2 Day 8 research blood 2-4 hours after ganetespib administration. Draw Cycle 2 Day 9 research blood 18-48 hours after ganetespib administration and on the same day as the cycle 2 research biopsy. The cycle 2 Day 9 research blood draw is required for all Arm B patients, including patients who do not undergo the cycle 2 research biopsy. If the Cycle 2 Day 8 dose is held for any reason

CONFIDENTIAL

This document is confidential. Do not disclose or use except as authorized.

(e.g. for toxicity), or if the Cycle 2 Day 8 biopsy is instead rescheduled to Cycle 2 Day 16, then draw the Cycle 2 research blood 2-4 hours after the Cycle 2 Day 15 dose of ganetespib and again 18-48 hours after the Cycle 2 Day 15 dose of ganetespib (i.e. on the same day as the cycle 2 research biopsy).

Complete a *DFCI 11-477 Specimen Requisition (Biopsy/Research Blood)* form (Appendix K). Fill the Streck tube completely and immediately mix by gentle inversion 8 to 10 times. Inadequate or delayed mixing may result in inaccurate results. Ship within 24 hours of collection at ambient temperature overnight to:

[name]
Dana-Farber Cancer Institute
[name]
[name]

Email [name] with the sample information and tracking information the day before shipping specimens: [contact]

Tube precautions:

- If samples cannot be shipped within 24 hours of collection, contact DFCI. DO NOT FREEZE OR REFRIGERATE TUBES as this could result in cfDNA breakage.
- Do not use tubes after expiration date.
- Fill the tube completely; overfilling or underfilling of tubes will result in an incorrect blood-to-additive ratio and may lead to incorrect analytic results.

See Appendix F for additional processing details specific to the laboratories at Dana Farber Cancer Institute.

Shipping note: Streck tubes samples are sent Ambient. Frozen and ambient specimens obtained and shipped on the same day to [name] (e.g., Progression or Off Study Biopsy Specimens, Streck Tubes, and Circulating Tumor Cells) may be placed in a combination shipping box which contains separate compartments for frozen and ambient samples. If a combination shipping box is not available, two shipping boxes should be used. Frozen samples shipped to [name]/Whitehead Institute obtained on the same day as these specimens must always be placed in a separate shipping box.

Lavender top tube

One 10 mL lavender top tube will be collected at baseline in order to extract germline DNA to be used as normal DNA reference for tumor tissue-based studies. If the sample is missed for any reason, it should be drawn at a future appointment. These collection tubes are provided by the Sponsor as needed.

Complete a *DFCI 11-477 Specimen Requisition (Biopsy/Research Blood)* form (Appendix K) and ship lavender top tubes at ambient temperature to:

CONFIDENTIAL

This document is confidential. Do not disclose or use except as authorized.

[name]
Dana-Farber Cancer Institute
[name]
[name]

Email [name] with the sample information and tracking information the day before shipping specimens: [contact]

PBMC analyses

For PBMC analyses, blood will be drawn directly into two PAXgene blood RNA tubes (ref #762165) from Qiagen/BD. PAXgene tubes will be collected at baseline (C1D1), C2 D8 and C2D9 (Arms A & B only), at progression/end of treatment and end of study. The Cycle 2 Day 9 sample should be collected as close as possible to 24 hours after the Cycle 2 Day 8 dose and not more than 48 hours after the C2D8 dose.

- **For Arm A patients:** The Cycle 2 Day 8 sample may be drawn +/- 3 days. Draw the Cycle 2 Day 9 research blood 18-48 hours after the Cycle 2 Day 8 research blood draw and on the same day as the cycle 2 research biopsy. If the Cycle 2 Day 9 biopsy is missed (i.e. due to scheduling problems, procedure cancellation, etc), then it should be performed instead on Cycle 2 Day 16 +/- 3 days, and the Cycle 2 research blood tests should be rescheduled to occur around the delayed biopsy (i.e. Cycle 2 Day 15 and Cycle 2 Day 16). If a patient on Arm A does not undergo the Cycle 2 biopsy, then the Cycle 2 Day 9 blood draw is not required. However, the patient is still required to undergo the Cycle 2 Day 8 research blood draw.
- **For Arm B patients:** Draw Cycle 2 Day 8 research blood 2-4 hours after ganetespib administration. Draw Cycle 2 Day 9 research blood 18-48 hours after ganetespib administration and on the same day as the cycle 2 research biopsy. The cycle 2 Day 9 research blood draw is required for all Arm B patients, including patients who do not undergo the cycle 2 research biopsy. If the Cycle 2 Day 8 dose is held for any reason (e.g. for toxicity), or if the Cycle 2 Day 8 biopsy is instead rescheduled to Cycle 2 Day 16, then draw the Cycle 2 research blood 2-4 hours after the Cycle 2 Day 15 dose of ganetespib and again 18-48 hours after the Cycle 2 Day 15 dose of ganetespib (i.e. on the same day as the cycle 2 research biopsy).

After the blood draw samples will sit at room temperature for two hours and then sit for 24 hours in a -20° C freezer. Following this, samples will be stored at -80° C until several samples have accumulated at which point samples will be shipped to [name] laboratory at the Whitehead Institute for Biomedical Research (Address below). A supply of PAXgene tubes will be shipped to participating sites as necessary. After the PBMC research blood draw, samples will sit at room temperature for two hours and then sit for 24 hours in a -20° C freezer. Following this, samples will be stored at -80° C until several samples have accumulated as tubes may be batched for shipping.

Complete a *DFCI 11-477 Specimen Requisition (PBMC Tubes)* form (Appendix K) and

CONFIDENTIAL

This document is confidential. Do not disclose or use except as authorized.

ship PBMC tubes on dry ice to:

[name]
Whitehead Institute
[name]
[name]

Circulating Tumor Cells

Blood samples for CTC analysis will be collected in two 7.5 mL (15mL total) CellSave tubes at baseline (C1D1), C2 D8 and C2D9 (Arms A & B only), at progression/end of treatment and end of study. The Cycle 2 Day 9 sample should be collected as close as possible to 24 hours after the Cycle 2 Day 8 dose and not more than 48 hours after the C2D8 dose.

- **For Arm A patients:** The Cycle 2 Day 8 sample may be drawn +/- 3 days. Draw the Cycle 2 Day 9 research blood 18-48 hours after the Cycle 2 Day 8 research blood draw and on the same day as the cycle 2 research biopsy. If the Cycle 2 Day 9 biopsy is missed (i.e. due to scheduling problems, procedure cancellation, etc), then it should be performed instead on Cycle 2 Day 16 +/- 3 days, and the Cycle 2 research blood tests should be rescheduled to occur around the delayed biopsy (i.e. Cycle 2 Day 15 and Cycle 2 Day 16). If a patient on Arm A does not undergo the Cycle 2 biopsy, then the Cycle 2 Day 9 blood draw is not required. However, the patient is still required to undergo the Cycle 2 Day 8 research blood draw.
- **For Arm B patients:** Draw Cycle 2 Day 8 research blood 2-4 hours after ganetespib administration. Draw Cycle 2 Day 9 research blood 18-48 hours after ganetespib administration and on the same day as the cycle 2 research biopsy. The cycle 2 Day 9 research blood draw is required for all Arm B patients, including patients who do not undergo the cycle 2 research biopsy. If the Cycle 2 Day 8 dose is held for any reason (e.g. for toxicity), or if the Cycle 2 Day 8 biopsy is instead rescheduled to Cycle 2 Day 16, then draw the Cycle 2 research blood 2-4 hours after the Cycle 2 Day 15 dose of ganetespib and again 18-48 hours after the Cycle 2 Day 15 dose of ganetespib (i.e. on the same day as the cycle 2 research biopsy).

Samples should be shipped overnight to the can sit at room temperature for up to 72 hours but must be mixed immediately with fixative to help prevent clotting and transferred to SuperFrost Plus slide as cytospin preparation. Leftover slides will be banked at -20 degrees C for future processing. A supply of CellSave tubes will be shipped to participating sites as necessary.

See Appendix C for additional processing details specific to the laboratories at Dana Farber Cancer Institute and Brigham & Women's Hospital.

Complete a *DFCI 11-477 Specimen Requisition (Archival Tissue Blocks/Slides and CTC Samples)* form (Appendix J) and ship CTC tubes at ambient temperature to:

CONFIDENTIAL

This document is confidential. Do not disclose or use except as authorized.

[name]
Dana-Farber Cancer Institute
[name]
[name]

Email [name] with the sample information and tracking information the day before shipping specimens: [contact]

Shipping note: Frozen and ambient specimens obtained and shipped on the same day to [name] may be placed in a vertical combination shipping box (containing separate compartments for frozen and ambient samples). If a vertical combination shipping box is not available, two shipping boxes should be used. Frozen samples shipped to [name]/Whitehead Institute obtained on the same day as these specimens must always be placed in a separate shipping box.

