- We will collect peripheral blood mononuclear cells (PBMC) pre-therapy, Cycle 2 Day 8, Cycle 2 Day 9, and time of progression. Using a Nanostring custom code set, we will assess a set of genes regulated by HSF1, the major transcriptional regulator of inducible expression for the entire heat shock network. We will also assess a panel of estrogen and ER-regulated genes, other downstream targets of Hsp90, and genes thought to play a role in malignant progression/endocrine resistance. We do not expect changes in estrogen and ER-regulated genes or genes thought to play a role in malignant progression/endocrine resistance, but will do this in order to have a consistent assay between PBMC samples and tumor samples as described above. We will describe gene expression over time upon exposure to fulvestrant or the combination of fulvestrant + ganetespib.
- We will describe the frequency of mutations in PIK3CA, ESR1, and other potential genes of interest in archival tumor specimens, cycle 2 Day 9 biopsy specimens, and at the time of progression (when available)
- We will explore the relationship between the presence of a PIK3CA and ESR1 mutations in archival tissue and PFS, in each arm separately
- We will describe mutations in PIK3CA, ESR1, and other potential genes of interest in circulating free DNA (cfDNA) at baseline and time of progression.
- We will explore the relationship between baseline mutations in PIK3CA and ESR1 in circulating cfDNA and PFS, in each arm separately.
- We will tabulate the PIK3CA and ESR1 mutations detected in cfDNA and tumor tissue in order to explore the level of agreement between these two methods
- We will bank any extra materials for future study. We anticipate that this annotated repository will be valuable for future research into the mechanisms of resistance to fulvestrant and to ganetespib.

CONFIDENTIAL

This document is confidential. Do not disclose or use except as authorized.

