5. TREATMENT PLAN

Treatment must begin within 7 days of randomization. Treatment will be administered on an outpatient basis. Expected toxicities and potential risks as well as dose modifications for fulvestrant and ganetespib are described in Section 6 (Expected Toxicities and Dosing Delays/Dose Modification). No investigational or commercial agents or therapies other than those described below may be administered with the intent to treat the participant's malignancy.

Patients who enter the study and who are postmenopausal on the basis of GnRH agonist treatment must continue that treatment throughout the duration of the study.

A total of 71 patients will be enrolled in the study. Patients will be stratified according to whether or not they have measurable disease (by RECIST 1.1) at baseline and then randomized 1:2 to the two treatment arms:

Arm A: Fulvestrant (n=24)

Arm B: Fulvestrant plus Ganetespib (n=47)

Patients who are randomized to Arm A may cross over to Arm C (Fulvestrant plus ganetespib) at the time of centrally confirmed progression.

In both Arms A and B, each cycle will be ~28 days in length. Treatment will continue until disease progression (possibly the second progression on the combination therapy, if the patient was originally randomized to Arm A fulvestrant), unacceptable toxicity, withdrawal of consent, or death, whichever comes first. Follow up (specifically, tumor measurements as scheduled in

CONFIDENTIAL

This document is confidential. Do not disclose or use except as authorized.

the protocol) will continue until disease progression, withdrawal of consent, death, or the start of other anti-neoplastic therapy, whichever comes first.

Minor schedule changes owing to observed holidays, inclement weather, etc. are permitted. Patients may interrupt therapy for protocol-directed reasons (i.e. toxicity). From Cycle 3 forward, patients may also interrupt therapy for personal preferences (e.g., holidays, vacations). Treatment should resume according to protocol guidelines. Patients may not voluntarily omit fulvestrant at any time. From Cycle 3 forward, patients may not voluntarily omit more than 2 doses of ganetespib in a single cycle, except as detailed below. See Section 9.0 Study Calendar for additional details.

It is anticipated that some patients in Arm B or Arm C may either choose or be taken off of ganetespib for reasons other than disease progression (i.e., for toxicity or patient preference). The following guidelines apply:

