9.5 SPECIMEN SUBMISSION REQUIREMENTS

The following specimens are to be submitted to the indicated lab or location. Refer to the information in sections 9.5.1-9.5.3 for specimen collection scheduling, billing, processing, and shipping instructions.

Specimen Type	Time Point							Shipping Condition	Ship to ^g
	Pre-Study	C1 D1 ^a	C2 D8	C2 D9	At time of progression ^c	Off-treatment without progression ^c	Off Study ^c		
Archival blocks (Section 9.5.1)	X							Ambient temperature	[name]
Optional biopsy (Section 9.5.2)	X				X (Arms A & B only)		X	OCT: Frozen (dry ice) Trizol (FNA): Ambient RPMI (FNA): ice/ice pack	[name]
Required biopsy (Section 9.5.2)				X (Arms A&B only)					
10 mL Streck tube (Section 9.5.3)		X ^b (Arms A & B only)			X ^f	X	X	Ambient temperature	[name]
10 mL Lavender top tube (Section 9.5.3)		X ^b (Arms A & B only)						Ambient temperature	[name]
PBMC collection (2 PAXgene tubes) (Section 9.5.3)		X (Arms A & B only)	X (Arms A & B only)	X (Arms A & B only)	X	X	X	Frozen (dry ice)	[name]/ Whitehead Institute
Circulating tumor cells (2- 7.5 mL CellSave tubes) (Section 9.5.3)		X (Arms A & B only)	X (Arms A & B only)	X (Arms A&B only)	X	X	X	Ambient temperature	[name]

- a. Samples may be collected at any time after documentation of written consent and confirmation of protocol eligibility, but BEFORE the first dose of protocol treatment. The best time to obtain this is on Cycle 1 Day 1.
- b. If baseline sample collection is missed for any reason, the sample should be drawn at a future appointment.
- c. Off-study blood samples should be drawn within 30 days of off-study. Time of progression blood samples may be counted as the “off study” blood sample if the patient is coming permanently off-study. Time of progression blood samples are drawn if patient progresses on Arms A or B (1st Regimen) or Arm C (2nd Regimen).

CONFIDENTIAL

This document is confidential. Do not disclose or use except as authorized.

Coded laboratory specimens will be stored in the Tumor Bank of the DFCI. These specimens will become the property of DFCI. Patients will be informed that their specimens may be used for research by investigators at DF/HCC and Whitehead Institute. Specimens will be identified with a sample ID number; all patient identifying material will be removed.

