10.1.8 Progression-Free Survival

Progression-free survival (PFS) is defined as the duration of time from start of treatment until time of progression or death, whichever comes first. Patients who stop protocol-therapy (either ganetespib or fulvestrant or both) for a reason other than progression or death should be followed for progression, as detailed in Study Calendar D until the patient progresses, initiates alternative anti-cancer treatment, dies, or withdraws consent, whichever comes first. If the initiation of non-protocol anti-cancer treatment occurs first, then the patient's PFS will be censored at the time of last disease evaluation before start of the non-protocol anti-cancer treatment.

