14.2 Primary Clinical Objective and Sample Size Justification

Progression Free Survival (PFS): Progression-free survival is defined as time from randomization until time of progression or death, whichever comes first. Patients who stop protocol therapy (either fulvestrant or ganetespib or both) for a reason other than progression or death should continue to be followed for progression per Study Calendar D. For subjects who do not progress or die, PFS will be censored at the time of last tumor evaluation before initiation of alternative anti-cancer treatment.

Analysis Population: All randomized patients will be included in the analysis of PFS. The analysis will be conducted based on intention to treat (ITT). However, data imputation will not be used for PFS. So patients with no follow-up at all will be censored for PFS at the date of randomization.

If the interim safety analysis indicates that the starting dose of ganetespib should be decreased to 175 mg/m², these patients will be combined with the patients who received a starting dose of 200 mg/m² in the ITT analysis. That is, all randomized patients will be included in the ITT analysis, regardless of starting dose and regardless of whether or not treatment was stopped early for any reason.

Power Calculation

The primary objective of this randomized, phase II study is to investigate whether ganetespib, when given in combination with fulvestrant, improves progression-free survival (PFS) compared to fulvestrant alone, in patients with ER-positive, metastatic breast cancer. This study will have a 1:2 randomization ratio: 24 patients will be randomized to Arm A (fulvestrant alone) and 47 patients will be randomized to Arm B (fulvestrant + ganetespib), for a total of 71 randomized patients. The expected accrual rate is ~3.5 to 4.5 patients per month over a period of ~20 months.

As this is an exploratory phase II study, no interim efficacy analyses are planned and there are no early stopping rules for efficacy (or lack of efficacy) in this study.

The primary comparison will be a one-sided log rank test of whether PFS is longer in patients randomized to Arm B (fulvestrant + ganetespib) than those randomized to Arm A (fulvestrant).

CONFIDENTIAL

This document is confidential. Do not disclose or use except as authorized.

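### The rule for replacing a missed baseline cfDNA (Streck) tube has no pre-dose limit, so on-treatment samples could be analysed as baseline in the exploratory PIK3CA/ESR1 analyses

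*Combined protocol and SAP*

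**What the plan says.** Section 9.5.3 assigns one Streck tube to cfDNA, drawn at baseline and at progression, and adds: "If the baseline sample is missed for any reason, it should be drawn at a future appointment". In the Section 9.5 specimen table, footnote b says the same: "If baseline sample collection is missed for any reason, the sample should be drawn at a future appointment". That footnote sits on two Cycle 1 Day 1 cells, Streck and lavender-top. The PBMC and circulating-tumor-cell cells in the same column do not carry it. Footnote a, on the column heading, allows collection at any time after consent and confirmed eligibility, "but BEFORE the first dose of protocol treatment".

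Section 1.4.2 gives the use: "We will explore the relationship between baseline mutations in PIK3CA and ESR1 in circulating cfDNA and PFS, in each arm separately". It also plans to describe cfDNA mutations at baseline and at progression. All objectives in 1.4.2 are labelled exploratory.

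PFS starts before any replacement draw under either definition. Section 14.2: "Progression-free survival is defined as time from randomization until time of progression or death, whichever comes first". Section 10.1.8 says PFS "is defined as the duration of time from start of treatment until time of progression or death, whichever comes first". The two origins are close, because Section 5 states: "Treatment must begin within 7 days of randomization".

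The last paragraph of Section 14.5 foresees a small number of Kaplan-Meier curves and log-rank tests for mutations against PFS, and possibly little more than tables of medians. It has no rule for late samples.

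**The concern.** The lavender-top tube supplies germline DNA, which does not change with treatment, so drawing it late costs nothing. The Streck tube supplies tumor-derived DNA and is meant to show the state before treatment. Giving both tubes the same replacement rule treats a time-dependent specimen as if it were fixed.

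A tube missed on Cycle 1 Day 1 would ordinarily be replaced after dosing has begun. Two things then happen together. The mutation call may reflect treatment, because tumor DNA has fallen below detection or a resistance mutation has been selected. And a patient whose replacement is drawn before progression has, by construction, been event-free from the PFS origin to that visit. At stake are the mutation-PFS association within each arm, the medians reported for the mutation groups, and the pre-treatment reference for the comparison with progression.

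**Working it through.** **1. The plan's own figure.** There is no stated power or sample size for the cfDNA analysis, so the only figure to reproduce is the primary design in Section 14.2, whose medians are used below. Inputs: exponential PFS, medians 4.0 and 8.0 months, 20 and 40 effective patients, 20 months' accrual (A) plus 20 months' follow-up (F), one-sided 0.05 log-rank test.

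Expected event fraction = 1 − [exp(−λF) − exp(−λ(A+F))]/(λA), with λ = ln 2/median.
- Arm A: 0.991 × 20 = 19.8
- Arm B: 0.916 × 40 = 36.6
- Total: 56.5, against 57 stated

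Schoenfeld power at 57 events and hazard ratio 0.5: √(57 × 1/3 × 2/3) × ln 2 − 1.645 = 0.822, which gives 79.4% against 80% stated. The design reproduces.

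**2. Built-in event-free time.** P(event before t) = 1 − exp(−ln 2 × t/median). Given no event by t, the median PFS from the origin is t + median. Months = days/30.4375.

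| Draw | t (months) | Arm A: event before t | Arm A: conditional median | Arm B: event before t | Arm B: conditional median |
|---|---|---|---|---|---|
| Cycle 3 Day 1 (56 days) | 1.84 | 27.3% | 5.84 (not 4.0) | 14.7% | 9.84 (not 8.0) |
| Cycle 5 Day 1 (112 days) | 3.68 | 47.1% | 7.68 | 27.3% | 11.68 |

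These count from Cycle 1 Day 1. If randomization was 7 days earlier, the Cycle 3 Day 1 values use t = 63/30.4375 = 2.07 months and become 30% and 16%. Before Cycle 3 the formula overstates the effect: imaging is every 8 weeks (Section 5.1.10), so an earlier event could be recorded only through death or unscheduled progression.

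**3. Does this bias the mutation contrast?** Single-arm simulation, 200,000 patients per setting, true mutant-to-wild-type hazard ratio 1, late tube available only if event-free at the draw, Cox model from the PFS origin. Assumptions not in the documents: 35% mutation prevalence; 10%, 20% or 40% of tubes late; draw at week 2, 8 or 16; 0%, 30% or 60% of mutations undetectable on treatment.

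| Late tubes kept as baseline | Arm A median (4 months) | Arm B median (8 months) |
|---|---|---|
| Pooled median PFS, range over grid | 4.04 to 5.24 | 8.03 to 9.33 |
| Hazard ratio, detection unaffected | about 1.00 | about 1.00 |
| Hazard ratio, 30% undetectable, largest | 1.07 | 1.03 |
| Hazard ratio, 60% undetectable, largest | 1.14 | 1.07 |

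The largest values occur with 40% late tubes drawn at week 16. With pre-dose tubes only, the hazard ratio stays between 0.99 and 1.02, which is 1.00 within simulation error. The mechanism is that late-tube carriers are called wild-type and take their event-free time into that group.

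**4. Can late tubes be recognised?** Appendix K records the collection date. Its time-point boxes are pre-study/baseline, Cycle 1 Day 1, Cycle 2 Day 8/9, off treatment, progression and off study. A replacement drawn at, say, Cycle 1 Day 15 or Cycle 3 Day 1 has no box of its own.

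**The case against.** Footnote b and Section 9.5.3 are collection rules. A reader might infer that on-treatment samples will certainly enter the baseline analysis, but no text says so. A future appointment could still fall before the first dose, which would satisfy both footnotes, and Section 9 asks for assessments to precede study medication. This stands: entry into the baseline set is inferred from the replacement wording together with the absence of an exclusion rule. It does not dispose of the point, since a tube missed on Cycle 1 Day 1 itself would normally be replaced after dosing.

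A reader might also infer that guaranteed event-free time biases the mutation contrast by itself. It does not. The analysis is within arm, the extra time goes to whichever mutation group the patient falls in, and the simulated hazard ratio stays at about 1.00 unless treatment changes the call.

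The formula also gives about 15% and 8% for a draw at Cycle 2 Day 1. Those figures should not be used, because no scheduled scan falls that early.

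Late tubes can be identified from the Appendix K date. True, but nothing tells the analyst to use it.

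Finally, a reader might infer that a few misclassified samples could overturn the result. No calculation supports that. The 20 and 40 in Section 14.2 are effective sizes for the primary test, not counts of cfDNA samples, and the number of missed tubes is unknown.

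**Conclusion.** The defect is real but minor. A rule suited to germline DNA has been applied to cfDNA, and nothing in Section 14.5 or Appendix K keeps a late Streck tube out of the baseline set.

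A late tube inflates the reported median of the group it joins: by 1.84 months for a Cycle 3 Day 1 draw among late-tube patients under the exponential model, and by less across the whole group. It biases the within-arm contrast only if treatment alters detection, reaching about 1.14 (Arm A median) or 1.07 (Arm B median) at the extreme of an assumed grid. These sizes assume exponential PFS, a replacement drawn before progression, and late-tube and detection rates that the documents do not give.

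It would be a mistake to extend the point to the trial's main conclusions. The primary PFS test, the secondary endpoints and the HSF1 analysis on archival tissue do not use this tube.

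**What to change.** In Section 9.5 footnote b and Section 9.5.3, keep the future-appointment rule for the lavender-top germline tube only. For the Streck tube, state that a sample counts as baseline only if drawn before the first dose of protocol treatment.

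Add one sentence to Section 14.5: Streck tubes drawn later are labelled on-treatment from the Appendix K collection date, may be banked, and are excluded from the baseline cfDNA-PFS analysis and the baseline-versus-progression description, with their number reported by arm. A sensitivity analysis that includes them can be added if wanted.

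The cost is one footnote, one line in Section 9.5.3 and one analysis sentence. The downside is that a few patients will have no baseline cfDNA result.
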